2. SYNOPSIS

Study Title	A multi-centre, randomised, controlled non-inferiority trial to compare the efficacy, safety and tolerability of Triple Artemisinin-based Combination Therapies versus first-line ACTs + placebo for the treatment of uncomplicated Plasmodium falciparum malaria in Africa
ACRONYM	DeTACT-Africa
Trial Design	A partially blinded randomised controlled non-inferiority trial comparing the efficacy, tolerability and safety of Triple ACTs artemether-lumefantrine+amodiaquine (AL+AQ) and artesunate-mefloquine+piperavaquine (ASMQ+PPQ) and the ACTs artemether-lumefantrine+placebo (AL+PBO), artesunate-mefloquine+placebo (ASMQ+PBO) (with single-low dose primaquine in some sites) for the treatment of uncomplicated Plasmodium falciparum malaria to assess and compare their efficacy, safety, tolerability.
Trial Participants	Subjects with acute uncomplicated P. falciparum malaria
Sample size	Estimated total sample size up to 3240 subjects recruited at 8 sites in Africa (Burkina Faso, DRC, The Gambia, Guinea, Niger, Nigeria, Rwanda, Tanzania) 
 - In Rwanda only – 216 subjects - All other sites – 432 subjects per site
Inclusion Criteria	
 • Male or female, aged ≥ 6 months to < 12 years (For Gambia, Rwanda sites only: ≥ 6 months) • Ability to take oral medication • Acute uncomplicated P. falciparum mono-infection • Asexual P. falciparum parasitaemia: 1,000/μL to $\leq 10\%$ parasitaemia, determined on a peripheral blood film (At Gambia, Rwanda sites only: For subjects ≥ 12 years – 1000/μL to 200,000/μL) • Fever defined as $\geq 37.5^{\circ}\text{C}$ tympanic temperature or a history of fever within the last 24 hours • Written informed consent by the subject or by the parent/guardian in case of children lower than the age of consent and assent if required (per local regulations) • Willingness and ability of the subjects or parents/guardians to comply with the study protocol for the duration of the study

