15. STATISTICAL CONSIDERATIONS

15.1. Sample size justification

These studies will have a non-inferiority trial design. Each site will be powered for the efficacy endpoint. For the safety and tolerability endpoint, the sample size will be pooled across the study

sites to achieve the desired power of at least 80% to detect rare events.

For sample size calculations, the following assumptions have been used: The expected efficacy of ACTs (AL, ASMQ) in these countries is expected to be approximately 96%. The matching TACT efficacy is assumed to be at least 90% under the null hypothesis of inferiority based on the WHO 90% efficacy threshold. However preliminary TRACII study data suggest that TACTs potentially may have a better efficacy of 1% to 2% higher in favour of TACT (i.e. a conservative 97%-98% efficacy or higher).

A one-sided alpha of 0.025 has been used in sample size calculations as non-inferiority is in one direction. For the efficacy outcome, a sample size of 60 subjects in the ACT plus placebo arms and 120 subjects in the matching TACT would be needed to achieve approximately 80% power to detect a non-inferiority margin difference between the group efficacy of -6%. With an additional 20% to cover for loss to follow up, we would therefore need 72 subjects in ACT plus placebo group and 144 subjects in the matching TACT in each of the sites. Since there will be 4 arms, it means we will need 432 subjects per site with 144 subjects in the two ACT arms combined and 288 subjects in the two TACT arms combined.

The sample sizes are in the ratio of 1:2 for ACT vs TACT to allow us to collect more safety and tolerability data for TACTs, which could be beneficial to both policy makers as well as future malaria patients [26, 27]. With these numbers of recruited subjects in Africa, we will have a power above 80% to detect an increase of the incidence of adverse events from 1 in 100 to 3 in 100 for subjects treated with ACT as compared to the matching TACT, respectively.

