For the safety and tolerability endpoints, we will perform a pooled analysis of the data obtained in the DeTACT-Africa and DeTACT-Asia. A total of 1707 subjects in ACT arms (918 and 789 subjects in the AL and ASMQ arms respectively) and 2787 subjects in TACT arms (1494 and 1293 subjects in the AL+AQ and ASMQ+PPQ arms respectively) recruited in both studies combined will allow us to detect increases of rare adverse events from incidences of 1 in 100 subjects to 3 in 100 subjects also with more than 80% power. The sample size calculations were performed using a specialized sample size calculation software, PASS 15.

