15.2. Statistical analysis

Analyses of other endpoints will be described in a Statistical Analysis Plan.

A brief overview is given below.

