15.2.1. Proportions

These will be compared using chi squared or Fisher's exact test, as appropriate. Crude proportions will be calculated with the exact 95% confidence intervals (CI), where relevant.

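### The Africa–Asia safety pool mixes 1:2 and 1:1 allocation, but the only tests named for adverse-event frequencies ignore trial and the SAP does not describe the pool

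*Protocol*

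**What the plan says.** Protocol 15.1 commits to a two-trial pool for safety and tolerability: "we will perform a pooled analysis of the data obtained in the DeTACT-Africa and DeTACT-Asia". It gives the combined ACT numbers as "918 and 789 subjects in the AL and ASMQ arms respectively" and the combined TACT numbers as "1494 and 1293 subjects in the AL+AQ and ASMQ+PPQ arms respectively", with more than 80% power for an adverse event rising from 1% to 3%. The paragraph before makes the same claim without Asia: "With these numbers of recruited subjects in Africa, we will have a power above 80" per cent.

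The African part is allocated 1:2. Protocol 15.1 plans "72 subjects in ACT plus placebo group and 144 subjects in the matching TACT in each of the sites", and Protocol 9.4 gives the matching randomisation ratio. The Synopsis has "Estimated total sample size up to 3240 subjects recruited at 8 sites in Africa": 216 in Rwanda, which has the AL pair only, and 432 at each of the other seven sites. Neither document states the Asian allocation.

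On method, Protocol 15.2 says "Analyses of other endpoints will be described in a Statistical Analysis Plan" and then gives an overview. For proportions, 15.2.1 says "These will be compared using chi squared or Fisher's exact test, as appropriate". Protocol 15.2.4 and SAP 3.4 name Fisher's exact test for adverse-event frequencies. The unpaired t-test in SAP 3.5 concerns QTc change only. None of these tests includes trial, region or site.

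The SAP describes an eight-country African study (section 2). Its section 2.2.1 repeats the sample-size text without the Africa–Asia paragraph, and DeTACT-Asia appears nowhere. SAP 3.4 pools over sites that gave the same treatment.

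**The concern.** When two trials with different allocation ratios are collapsed into one two-by-two table, the arms no longer hold the same mix of trials. Randomisation within each trial does not repair this. Any difference in background event rate between Africa and Asia then enters the crude TACT-versus-ACT contrast. Such a difference could come from age, transmission, event ascertainment or local practice. If Asia's rate is higher, the contrast hides harm from the TACT. If Africa's is higher, it exaggerates harm.

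Safety is a secondary objective, but more TACT safety data is the protocol's stated reason for the 1:2 ratio, and the two-trial pool is the largest safety comparison planned. Neither document says how that pool will be tested, so the choice between a crude and a stratified result could be made after the data are seen.

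**Working it through.** **Step 1. The plan's own figure.** Normal approximation with pooled variance under the null, two-sided 5%, AL pair: n = 918 and 1,494, p = 0.01 and 0.03.

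- Mean rate: (9.18 + 44.82)/2,412 = 0.0224.
- Null SE: √[0.0224 × 0.9776 × (1/918 + 1/1,494)] = 0.00620.
- Alternative SE: √(0.0099/918 + 0.0291/1,494) = 0.00550.
- Power: Φ[(0.02 − 1.96 × 0.00620)/0.00550] = Φ(1.425) = 92.3%.

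The same calculation for 789 and 1,293 gives 87.8%. The stated power of more than 80% for the pool is reproduced.

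**Step 2. Asian arms by subtraction.**

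| Arm | Pool (Protocol 15.1) | Africa | Asia | Asia's share |
|---|---|---|---|---|
| AL | 918 | 8 × 72 = 576 | 342 | 37.3% |
| AL+AQ | 1,494 | 8 × 144 = 1,152 | 342 | 22.9% |
| ASMQ | 789 | 7 × 72 = 504 | 285 | 36.1% |
| ASMQ+PPQ | 1,293 | 7 × 144 = 1,008 | 285 | 22.0% |

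The African arms sum to 3,240, the stated total. Asia comes out at exactly 1:1 in both pairs.

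**Step 3. Bias of the crude difference.** Let s be Asia's share of an arm. With no drug effect the crude rate in that arm is (1 − s) × Africa rate + s × Asia rate. Hence:

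crude TACT − ACT = (s_TACT − s_ACT) × (Asia rate − Africa rate)

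The coefficient is 342/1,494 − 342/918 = −0.144 for the AL pair and 285/1,293 − 285/789 = −0.141 for the ASMQ pair. For example, with 5% in Africa and 15% in Asia, the AL pair shows 8.7% on ACT and 7.3% on TACT, an apparent 1.4-point benefit with no drug effect.

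**Step 4. False rejection with no drug effect** (two-sided 5%). All rates are assumptions, one per trial. The Fisher figures are exact enumerations of the pooled counts. CMH stratified by trial (200,000 simulated trials, no continuity correction) gave 5% in every row.

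| Africa/Asia rate | AL pair, crude Fisher | ASMQ pair, crude Fisher |
|---|---|---|
| 1%/3% | 7.5% | 7.0% |
| 3%/1% | 5.8% | 5.4% |
| 10%/15% | 7.9% | 7.3% |
| 15%/10% | 7.3% | 6.8% |
| 5%/10% | 10.0% | 9% |
| 10%/5% | 8.4% | 8% |
| 5%/15% | 23.5% | 20.0% |
| 15%/5% | 16.9% | 14.5% |
| 10%/30% | 45.6% | 39.1% |
| 30%/10% | 34.6% | 29.1% |

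With equal rates of 1% the AL pair gives 3.8%. At the large gaps nearly all false rejections favour TACT when Asia's rate is higher, and go against TACT when Africa's is higher.

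**Step 5. Detection of a true TACT excess.**

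| Pair, true risk ratio | Africa/Asia ACT rate | Crude Fisher | CMH by trial |
|---|---|---|---|
| AL, 1.3 | 10%/15% | 44% | 67% |
| AL, 1.3 | 15%/10% | 89% | 75% |
| AL, 1.5 | 5%/10% | 52% | 80% |
| AL, 1.5 | 10%/5% | 98% | 90% |
| AL, 2 | 1%/3% | 41% | 70% |
| AL, 2 | 3%/1% | 95% | 86% |
| ASMQ, 1.3 | 10%/15% | 39% | 60% |
| ASMQ, 1.3 | 15%/10% | 84% | 68% |
| AL, 3 | 1%/3% | 95% | 99% |
| ASMQ, 3 | 1%/3% | 92% | 98% |

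Where the crude test looks better, bias produces the gain. For the AL pair with a true ratio of 1.3, the crude ratio is 1.37 at 15%/10% and 1.22 at 10%/15%.

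**Step 6. Secondary point: non-matching comparisons.** Rwanda supplies 72/576 = 144/1,152 = 12.5% of each African AL arm and no ASMQ subjects. For AL+PBO versus ASMQ+PPQ in Africa alone, with no effect and a 10% rate elsewhere, crude Fisher rejects in about 4%, 6% and 11% of trials when Rwanda's rate is 10%, 15% and 20%. The single-pair sites that Protocol 7 permits could move this imbalance either way.

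**The case against.** The strongest reply is that no wrong test has actually been specified. The commitment to pool stands under sample size, the tests are introduced as a brief overview, and the SAP covers Africa, where matching pairs are 1:2 at every site and Fisher's test is not confounded by site. The pool may be specified in the Asian trial's documents or in an integrated plan. The 1:1 ratio is derived from planned totals, and stratifying by trial would not be enough if Asian sites used different ratios. The pool is sized for rare events, where the distortion is small, and the large error rates need assumed gaps of 10 to 20 percentage points. Both documents also promise safety comparisons within and across sites and regions, which would bring a background difference to light.

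Much of this stands as a limit on size and certainty. Applying Fisher's test to the pool is an inference from 15.1 and 15.2.4, and the rates are assumed. It does not remove the point. The pool is a stated commitment, the only tests named for its endpoint ignore trial, and neither document refers to another plan for it. The SAP announces separate plans for several other analyses, but not for this one. Descriptive results by region would reveal a background difference without correcting the pooled test. Nor is the pool confined to rare events: Protocol 19.4.1 puts vomiting and anorexia each at about 18% on AL, and 19.4.3 reports at least one adverse event in 49% on ASMQ. Moderate effects on common events are where masking is material.

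**Conclusion.** The concern holds and should be fixed. The protocol commits to a pool in which trial is associated with arm, and it names no test that accounts for trial. Applied to that pool, the named test gives a contrast biased by about −0.14 times the Asia-minus-Africa rate difference. False rejection rises little for modest gaps (about 5% to 10% in the cases tried) and substantially for large ones. The more serious consequence is masking: when Asia's background rate is higher, power for moderate true excesses falls by about 20 to 30 percentage points in the cases tried.

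This rests on the planned arm sizes, on Asia being 1:1 as subtraction implies, on the named test being used for the pool, and on assumed rates. With equal rates there is no bias. Detection of a threefold increase remains above 90% at 1%/3%. Matching comparisons within Africa are unaffected. The Rwanda point is secondary and smaller.

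**What to change.** Add to Protocol 15.2.4 and SAP 3.4 wording such as:

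> Any safety comparison that pools DeTACT-Africa and DeTACT-Asia will use a Cochran-Mantel-Haenszel test (exact version for sparse data) stratified by trial, or by site if allocation ratios differ between sites, with a stratified risk difference or risk ratio and its 95% CI. African and Asian results will be shown beside the pooled result.

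If the pool is to have its own analysis plan, say so and cite it. Fisher's test can stay for matching pairs within Africa. For the secondary point, add:

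> Non-matching comparisons will use only sites, and periods, in which both arms were randomised concurrently.

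The cost is wording and routine code, with no new data. If the trials have equal rates, stratifying loses no power: at 1%/1% with a risk ratio of 3, crude Fisher and CMH give 92.5% and 92.9% (AL pair) and 88.0% and 88.7% (ASMQ pair). An exact stratified test may be slightly more conservative, and strata without events add no information. Restricting the non-matching comparisons drops Rwanda's 72 AL+PBO and 144 AL+AQ subjects from those comparisons only.

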15.2. Statistical analysis

Analyses of other endpoints will be described in a Statistical Analysis Plan.

A brief overview is given below.

15.2.1. Proportions

These will be compared using chi squared or Fisher's exact test, as appropriate. Crude proportions will be calculated with the exact 95% confidence intervals (CI), where relevant.

15.2.2. Continuous data

These will be summarised by medians (IQR, ranges) and means (standard deviations, 95% CIs), as appropriate, and will include the parasite counts and laboratory parameters. Comparisons of continuous data will be assessed using the paired/unpaired t tests or the sign rank/Mann Whitney U tests, as appropriate.

Analyses of the parasite clearance data will be conducted to look for geographical and temporal differences.

15.2.3. Pharmacokinetic data

Pharmacokinetic parameters such as C_{max} , T_{max} and AUC of artemether, lumefantrine, amodiaquine, artesunate, piperaquine, and mefloquine (and their metabolites) will be estimated using nonlinear mixed-effects modelling. All available study data will be pooled and integrated for a population modelling approach for an in-depth analysis of the pharmacokinetic properties of the above drugs as well as their relationship to treatment outcomes (i.e. safety and efficacy outcomes).

15.2.4. Safety analysis

Safety analyses will be based on the whole population that get administered the study drug. Safety and tolerability of TACTs versus ACTs will be assessed by comparing the frequency (%) of adverse events and serious adverse events, with particular attention to abdominal pain, appetite perturbation, biochemical markers of hepatic and renal toxicity and QT interval prolongation, using the Fisher's exact test. Safety data will be presented in tabular and/or graphical format and summarized descriptively. Any clinically relevant abnormalities or values of potential clinical concern will be described. Subjects will be analysed according to an intention to treat and a per protocol method where appropriate.

16. DIRECT ACCESS TO SOURCE DATA/DOCUMENTS

Direct access will be granted to authorised representatives from the sponsor and host institution and the regulatory authorities and ethical committees, if applicable, to permit trial-related monitoring and inspections.

17. QUALITY CONTROL AND QUALITY ASSURANCE PROCEDURES

The study will be conducted in accordance with the current approved protocol, ICH GCP, any national regulations that may apply to this study and standard operating procedures. The Clinical Trials Support Group (CTSG) or their designees will be engaged in assuring QA/QC of study execution in collaboration with the WWARN Asia Regional Centre. Their role will include but not be limited to monitoring adherence to WIs for collection of clinical data and laboratory specimens and quality checks (curation) of clinical and laboratory data according to standard methodologies. Malaria slide QC will be performed by WWARN. A project steering committee will oversee the project.

17.1. Monitoring

Study sites may have in place a system for internal monitoring. In addition, regular external monitoring of all sites will be coordinated by the MORU CTSG according to ICH GCP and a Monitoring Plan. Data will be evaluated for compliance with the protocol and accuracy in relation to source documents. The monitors will check whether the clinical trial is conducted and data are generated, documented and reported in compliance with the protocol, GCP and the applicable regulatory requirements. Evaluation of on-site monitoring schemes, such as a reciprocal monitoring scheme, may be undertaken at selected sites by CTSG and WWARN.

18. DSMB AND PROJECT STEERING COMMITTEE

18.1. DSMB

An independent Data Safety and Monitoring Board (DSMB) will be set up consisting of qualified volunteers with the necessary knowledge of clinical trials. The DSMB will receive summary reports, prior to each meeting. All data reviewed by the DSMB will be in the strictest confidence. A DSMB charter will outline its responsibilities and how it will operate.

The DSMB will meet formally at the following timepoints:

- before the study starts
- after the first 100 subjects have been accrued into the study
- after the first 500 subjects have been accrued into the study
- At additional time-points before the planned interim analyses, as indicated by the DSMB after their review, if deemed necessary

- At the end of the study (i.e. after the last patient has finished follow up)

Unscheduled meetings can be held on the initiative of the Medical Monitor (Contact details will be summarized in DSMB Charter and investigators site file), Principal Investigator or DSMB to consider e.g. serious adverse events as they are reported OR if an earlier safety review is thought to be indicated.

19. ETHICS

19.1. Declaration of Helsinki

The Investigator will ensure that this study is conducted in compliance with the current revision of the Declaration of Helsinki (Fortaleza 2013).

19.2. ICH Guidelines for Good Clinical Practice

The Investigator will ensure that this study is conducted according to any National Regulations and that it will follow the principles of the ICH Guidelines for Good Clinical Practice.

19.3. Approvals

The study protocol and its associated documents will be submitted to the Oxford Tropical Research Ethics Committee (OxTREC) and the appropriate local ethics committees for written approval. If required by participating countries Regulatory Authority, the protocol will also be submitted for approval. The Investigator will submit and, where necessary, obtain approval from the above parties for all substantial amendments to the original approved documents.

19.4. Risks

This study will use drugs that have been studied thoroughly and their toxicities are well described. In general, they are all well tolerated.

19.4.1. Risks of artemether-lumefantrine

Reported AL side effects have generally been mild. The main side effects are GI upset: anorexia (~18%), nausea (~5%), vomiting (~18%), abdominal pain (~5%), and diarrhoea (~10%), headache (~10%), dizziness (~4%), fatigue (~1%) and sleep disturbance (~2%). Other symptoms reported infrequently include palpitations, myalgia, arthralgia (all of which could be disease related), and rash. AL does not cause prolongation of the QTc interval.

19.4.2. Risks of amodiaquine

The main side-effects of amodiaquine are nausea, vomiting and fatigue which are mild to moderate in nature. When the drug was used for prophylaxis, rare adverse reactions of agranulocytosis and hepatotoxicity were observed.

19.4.3. Risks of artesunate-mefloquine

Side effects such as nausea and vomiting, dizziness and headache have shown to be consistently associated with ASMQ. Other adverse effects following treatments with ASMQ are fatigue, nightmares and anxiety. Palpitations are also relatively more common with AS+MQ. Mild prolongations of QTc intervals have been reported following ASMQ treatments but these are less frequent as compared to DHA-PPQ. From an individual patient meta-analysis of 5,487 subjects treated for *P. falciparum* with ASMQ, 49% of patients had at least one adverse event, 3.4% of subjects had early vomiting and the incidence of serious neurological reaction was 2 per 1,000.

19.4.4. Risks of piperazine

Piperazine is generally very well tolerated. Occasional abdominal discomfort and diarrhoea have been reported in clinical trials of DHA-PPQ which may have resulted from piperazine. Although piperazine slightly prolongs the electrocardiogram QT interval, there is no evidence for clinically significant cardiovascular toxicity at the doses which will be administered in this study.

19.4.5. Risks of new partner drug combinations

No interactions between lumefantrine and amodiaquine or piperazine and mefloquine are expected. Based on the relatively safe and limited side effect profiles of both drugs, no life-threatening interactions between lumefantrine and amodiaquine are expected. Also no life-threatening interactions between piperazine and mefloquine are expected.

In addition, the preliminary results of the TRACII trial indicate that the TACTs artemether-lumefantrine+amodiaquine and DHA-piperazine+mefloquine have a good safety and tolerability profile, although both TACTs were found to induce slightly higher vomiting rates within the first hour after administration of the study drugs, compared to their matching ACTs. The safety profile of ASMQ +/- PPQ is expected to be similar to that of DHA-PPQ +/- MQ.

19.4.6. Risk of phlebotomy & finger stick

The primary risks of phlebotomy include local discomfort, occasional bleeding or bruising of the skin at the site of needle puncture, and rarely haematoma or infection.

19.5. Benefits

Malaria is a disease that needs to be treated promptly. All subjects will benefit from receiving efficacious treatment at no cost. They will be followed up closely and will be given rescue treatment if clinically indicated.

19.6. Alternatives to study participation

Subjects are able to decline freely participation in this study. If so, they will receive standard care for their malaria.

19.7. Incentives & Compensation

Study subjects or their guardian in the case of children will be compensated for time lost from work. Subjects and/or their guardians will be reimbursed for the time lost from work as a result of hospitalisation, the cost of local transport to attend for the follow up visits and will receive meals or a per diem to cover the costs of meals on those days. The amounts in monetary terms will be determined by each site. The study will pay for treatment for drug-related SAEs or other research-related injuries. The study cannot pay for long term care for disability after hospital discharge resulting from complications of the illness.

